High ADR (eg, $\geq 20\%$) has been associated with a reduced risk of interval CRC [14,15]. Methods that can improve polyp detection in the right colon such as retroflexed examination of the right colon, second forward view examination of the right colon, use of colonic fold flattening device, colonoscope with an increased field of view may potentially reduce the risk of interval CRC, but data is still limited [16-20]. Performance of a second forward view (SFV) examination of the right colon may be the easiest and safest from a practical standpoint when compared to other options (eg, additional training is often needed for retroflexed examination of the right colon since there may be a potentially higher risk of perforation in endoscopists not familiar with the technique, additional equipment is needed when using a colonic fold flattening device, or a colonoscope with an increased field of view). In a recent randomized control study comparing retroflexed examination and SFV examination in the right colon in patients undergoing screening or surveillance colonoscopy, high ADRs were achieved by both methods (47% in retroflexed group vs 46% in SFV group, $p = 0.75$) [17]. A recent single arm prospective cohort study of 280 male veteran patients in USA showed that additional adenomas were detected in 15.4% of the patients after a SFV examination of the right colon [18]. The overall ADR increased by 3.2% and the ADR for the right colon increased by 6.7% after SFV examination of the right colon [18]. 3.6% of the patients had a change in their screening / surveillance interval with the addition of findings on the SFV examination of the right colon [18]. Of note, the overall ADR in this cohort of male veteran patients was very high and up to 71.8% on conventional withdrawal exam [18]. It is unclear whether a SFV examination of the right colon would still be beneficial in populations with both males and females and a lower overall ADR (eg, closer to the

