The risk of harm or discomfort of the second forward view examination of the right colon is similar to the risks of standard colonoscopy (less than 1% chance of perforation, bleeding, etc) because it does not involve a new endoscopic skill or new equipment. Based on local data at the Prince of Wales Hospital, the second forward view examination of right colon takes about an additional 2 minutes. No additional sedation medication was needed for the added time based on the local data.

Randomization Method

Block randomization generated by a computer program will be used at study site. Randomization will be in 1:1 ratio.

OUTCOME MEASURES

Primary Outcomes

- 1) Per-patient ADR in the right colon in each group. For the SFV group, it is defined as the number of patients with at least 1 adenoma identified in the right colon on either the first or second examination of the right colon divided by the total number of patients in the SFV group. Thus, if a patient has at least 1 adenoma detected on both the first examination and the second examination of the right colon, then this patient will be counted once only. For the conventional group, it is defined as the number of patients with at least 1 adenoma identified in the right colon on the conventional withdrawal examination of the right colon divided by the total number of patients in the conventional withdrawal group.

Secondary Outcomes

- 1) Increase in per-patient ADR in the right colon in the SFV group.
 - It is defined as the difference between the new ADR in the right colon after the first examination and SFV (again, if a patient has at least 1 adenoma detected on both the first examination and the second examination of the right colon, then this patient will be counted once only) and the ADR in the right colon after the first examination.
- 2) Overall ADR for the entire colon in each group.
 - For the SFV group, it is defined as the number of patients with at least 1 adenoma identified on either the second examination of the right colon or on the first examination of the right + examination from hepatic flexure to rectum, divided by the total number of patients in the SFV group. Thus, if a patient has at least 1 adenoma detected on both the first examination and

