Based on an ADR in the right colon of 16.0% from a screening colonoscopy cohort in Hong Kong, and assuming a SFV examination of the right colon would give a 6.7% increase in ADR in the right colon [18], we would need 502 patients per study group (ie, a total of 1004 patients for the study) in order to give a power of 80% at a type 1 error of 5%.

STATISTICAL ANALYSIS

Categorical variables will be analyzed using chi-square test or Fisher's exact test. Continuous variables will be analyzed using Student's t-test or Mann-Whitney U test. $P < 0.05$ is considered to be statistically significant.

TIME TABLE OF WORK

The ethics committee's approval of the study will be sought. The study will commence in November / December 2016 upon ethics committee's approval. The expected project duration is 24 months.

DATA HANDLING AND DISSEMINATION OF INFORMATION

All data obtained from the study will be kept confidential and be available only to personnel involved in the study and patient care. Case report forms and other documents will be kept in designated area of the Institute of Digestive Disease and retained for 7 years after study completion. The results of this study will be presented in scientific meetings and medical journals.

DISCLOSURE

The study would be conducted in compliance with the Declaration of Helsinki.

REFERENCE

1. World Health Organization. International Agency for Research in Cancer. Globocan 2012: estimated cancer incidence, mortality and prevalence worldwide 2012.
2. Hong Kong Cancer Registry. Leading Cancer Sites in Hong Kong in 2013, Hong Kong: Hospital Authority. Retrieved on 1st August 2016 from http://www3.ha.org.hk/cancereg/rank_2013.pdf

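### 502 patients per group gives about 77% power for 16.0% versus 22.7%, not the stated 80%; that target needs 545 per group

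*Combined protocol and SAP*

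**What the plan says.** Everything needed for the calculation is in the combined protocol and SAP.

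- **Control rate** (Sample Size Calculation): "Based on an ADR in the right colon of 16.0% from a screening colonoscopy cohort in Hong Kong".
- **Effect** (same section): "assuming a SFV examination of the right colon would give a 6.7% increase in ADR in the right colon". The background section traces this figure to a single-arm cohort of 280 male veterans.
- **Operating characteristics** (same section): "in order to give a power of 80% at a type 1 error of 5"%. The section does not say whether the test is one- or two-sided.
- **Result** (same section): "we would need 502 patients per study group (ie, a total of 1004 patients for the study".
- **Allocation** (Randomization Method): "Randomization will be in 1:1 ratio".
- **Test** (Statistical Analysis): "Categorical variables will be analyzed using chi-square test or Fisher's exact test", with significance declared at P < 0.05.

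No allowance for dropout, no continuity correction and no rounding of the second-forward-view (SFV) rate is mentioned.

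**The concern.** A reader who puts the stated inputs into a standard formula does not get 502. The number is too small for the power claimed, and this calculation is the plan's only justification for enrolling 1,004 people.

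The stake is how a non-significant primary result would be read. It would be presented as coming from a trial with a 20% planned chance of missing a 6.7-point gain, when that chance was about 23%. There is no cushion either. A true gain below 6.7 points would have less than 77% power, and the background section itself questions whether the benefit carries over to populations with lower ADRs.

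**Working it through.** **Inputs.** p1 = 0.160. d = 0.067, so p2 = 0.227. Power is 80% (z = 0.8416), the type 1 error is 5%, and allocation is 1:1. Two-sided testing (z = 1.9600) is an assumption, taken as the usual default. The 6.7% is read as percentage points: a relative increase would give 17.07% in the SFV group and need 18,852 per group.

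**Formula (pooled variance under the null), n per group:**

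n = [z₀.₉₇₅ √(2 p̄ q̄) + z₀.₈₀ √(p1q1 + p2q2)]² / d²

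**Attempt to reproduce 502 from the stated inputs.**

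- p̄ = (0.160 + 0.227)/2 = 0.1935, so 2p̄q̄ = 0.3121 and its square root is 0.5587.
- p1q1 + p2q2 = 0.1344 + 0.1755 = 0.3099, with square root 0.5567.
- Numerator: (1.9600 × 0.5587 + 0.8416 × 0.5567)² = (1.0950 + 0.4685)² = 2.4445.
- n = 2.4445 / 0.004489 = 544.5, rounded up to **545**.

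**Other standard variants, same inputs:**

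| Method | n per group |
|---|---|
| Two-sided, pooled variance | 545 |
| Two-sided, unpooled variance | 542 |
| Two-sided, arcsine | 542 (542.02 before rounding) |
| Two-sided, 2p̄q̄ throughout | 546 |
| Two-sided, continuity-corrected | 574–575, depending on rounding |
| One-sided, pooled variance | 429 |
| One-sided, continuity-corrected | 459 |

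None gives 502.

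**What does give 502.** Put p2 = 0.23 (d = 0.070) into the pooled two-sided formula:

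- p̄ = 0.195, 2p̄q̄ = 0.3140, p1q1 + p2q2 = 0.3115.
- n = (1.0982 + 0.4697)² / 0.0049 = 2.4584 / 0.0049 = 501.7, rounded up to **502**.

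**Power at 502 per group for 16.0% versus 22.7%.**

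- z = [0.067 × √502 − 1.9600 × 0.5587] / 0.5567 = (1.5012 − 1.0950) / 0.5567 = 0.730, so power = **76.7%**.
- Exact enumeration of the Pearson chi-square test gives 76.9%; the unpooled and arcsine approximations also give 76.9%.
- As a side case, the continuity-corrected chi-square gives 74.5%.
- Check at 545 per group: power 80.0%.

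**Size of the gap.**

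- 545 − 502 = 43 per group, 86 in total: 7.9% of the 545 required, or 8.6% of the 502 planned.
- At 502 per group and a 16.0% control rate, the difference detectable with 80% power is 7.0 points, not 6.7.

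**The case against.** The strongest reply accepts the arithmetic and says that it matters little. Three points of power and 0.3 points of detectable difference are small beside the uncertainty in the inputs. With 502 per group and a 6.7-point gain, power is 80.1% at a 14% control rate and 73.6% at 18%. With the control rate held at 16.0%, it is 63.7% for a gain of 5.7 points and 86.5% for 7.7 points. A null result would in any case be judged mainly from its confidence interval. This argument stands as to size. It does not rescue the statement, because uncertainty about an assumption does not excuse a wrong result computed from it.

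Three narrower objections deserve an answer.

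- **Sidedness is not stated.** With a one-sided 5% test, power at 502 would be 85.2%. So the 77% is conditional on a two-sided test. But one-sided testing needs only 429, so it does not explain 502. Adding about 15% dropout to it gives 429/0.85 ≈ 505, which is near but not equal, and the plan states neither element.
- **Rounding to 23% is an inference.** That is correct: the document never gives 23%, and another undocumented pair, 14.0% versus 20.7%, comes to 501. The exact match makes rounding probable, not proven. The discrepancy does not depend on its cause.
- **Fisher's exact test is unlikely to be needed.** Also fair. At 502 per group the expected counts are about 80 and 114 patients with an adenoma, so nothing is sparse. The 74.5% figure is a side case and the conclusion does not use it.

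**Conclusion.** The concern holds. Under the plan's own inputs, 502 per group does not deliver 80% power. It delivers about 77% (76.7% by normal approximation, 76.9% by exact enumeration of the chi-square test), and 80% requires 545 per group. This rests on a two-sided 5% test, a 6.7-point absolute gain, 1:1 allocation and no losses. The statement is wrong as written, but the practical effect is modest, and neither the outcome definition nor the validity of the test is touched.

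**What to change.** Rewrite the sample size sentence so that its inputs and output agree, name the chi-square test, say that it is two-sided, and give the assumed SFV rate explicitly. There are three consistent versions:

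1. **Keep 502 and the 6.7-point effect.** With 502 patients per group, a two-sided 5% chi-square test has about 77% power to detect 16.0% versus 22.7%.
2. **Keep 502 and 80% power.** The design effect is then 7.0 points (16% versus 23%). This needs its own justification, because the cited cohort supplies 6.7.
3. **Keep 80% power for 6.7 points.** The requirement is 545 per group, 1,090 in total.

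The first is the simplest. Versions 1 and 2 cost one sentence and no extra patients; version 1 makes the stated power slightly less favourable. Version 3 adds 86 patients.
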